#### *b. Secondary Outcomes*

The proportion of rescue narcotics will be compared between the ketorolac and placebo groups. Narcotics will be converted to standard morphine equivalents for statistical comparison.

On day two, the research fellow will also ask patient's his/her Global Evaluation of Study Medication by telephone. The patient will be asked, "How would you rate the study medication you received to delay pain". The choices will be on a four point scale: 1=poor; 2=fair; 3=good; 4=excellent.

Adverse events will be obtained from a standard form included in the patient's study diary. The proportion of adverse events will be compared between the ketorolac and placebo groups.

Time to regular shoe gear will be compared between the two groups. This information will be assessed during the post-operative visits and recorded within the secure BIDMC online medical record for each patient. Level of post-operative activity will also be evaluated with the help of the functional recovery index. This is a validated instrument for post-operative patients which includes three main domains: 1. Pain and social activity; 2. Lower limb activity; 3. General physical activity.

Summary statistics will be analyzed and reported. Continuous data will be analyzed with a 2-sided student's t-test if normally distributed or a Wilcoxon Rank Sum test if it cannot be justified through the Central Limit Theorem. From this data, confidence limits will be obtained and a 2-sided p value of  $\leq 0.05$  from the Fisher Exact Test will be considered statistically significant. If there are significant confounders identified, multivariate regression or stratification may be required and utilized if necessary. Binary data points will be compared by chi square analysis. From this, 95% confidence intervals will be obtained as well as a p-value from the Fisher Exact Test. A compliers-only analysis will also be secondarily performed if necessary, with the notion that this part of the study may have confounders and will not be part of the randomized comparison. Table 1 of the study will detail subject ages, gender, comorbidities, and other baseline study demographics.

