**B1. PURPOSE OF PROTOCOL**

The purpose of this study is to evaluate the effects of ketorolac (30 mg IV dose intra-operatively followed by 10 mg orally every 8 hours for five days) together with standard of care in pain control, compared to placebo (one pill every 8 hours for five days) plus standard of care, in patients undergoing Kalish bunionectomies. Long-term outcomes of bunionectomy procedures will also be evaluated including radiographic healing, adverse events, and time to regular shoe gear and activities up to a six month period.

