Pain will be measured by both unidimensional and multidimensional instruments. The McGill Pain Questionnaire – Short Form (MPQ-SF), Visual Analog Scale (VAS), pain medication related information, and study protocol compliance information will be collected at this time. The research fellow will instruct patients on how to fill out the visual analog scale (VAS) in the study diary. The VAS will be pre-printed in a diary that is given to the patient post-operatively. The VAS will have the end anchors, “no pain” and “worst possible pain”. If patient compliance with the VAS is greater than 95%, then the VAS will be used for the primary analysis. As a back-up, the MPQ-SF will be utilized as the primary analysis.

*d. Week One:* Patients will be evaluated in the clinic by his/her surgeon and re-banded. Patient diaries will be collected, post-operative medications will be counted, and study compliance will be verified.

*e. Week Two:* Sutures will be removed if appropriate and the patient may begin to get the surgical site wet. A soft bunion splint will be given to maintain soft tissue correction and is worn with the post-operative shoe for one more week. Range-of-motion exercises will be initiated and patients can be weight bearing as tolerated.

*f. Weeks Three through Five:* Anteroposterior and lateral foot radiographs will be taken at week three  $\pm$  one week. If the surgeon determines there is satisfactory healing, the patient will be transitioned to a supportive soft-soled shoe to initiate a propulsive gait. Range-of-motion exercises will be continued. The soft removable bunion splint is worn at bedtime for another 1-2 weeks.

*g. Week Six  $\pm 1$  week:* Weight bearing anteroposterior and lateral foot radiographs will be taken and the patient will be clinically assessed. If there is satisfactory healing, as determined by the surgeon, the patient can transition to normal activities. High impact activities, such as running or

jumping, will be avoided until the eighth week following surgery. Physical therapy will only be initiated if the surgeon determines its necessity. Indications for physical therapy may include a continued stiff joint or chronic edema.

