*h. Week Twelve and Subsequent Visits:* Weight bearing anteroposterior and lateral foot radiographs will be taken and the patient will be clinically assessed at week twelve  $\pm$ 1 week. If there is complete osseous union on radiographs, the patient will have completed the study. If there is incomplete osseous union on radiographs, the patient will continue to be followed by his/her surgeon. The timing and frequency of these subsequent visits will be determined by the patient's surgeon.

If there is incomplete osseous union after twelve weeks, the patient will be classified as a delayed union. If there is incomplete osseous union after six months, the patient will be classified as a nonunion.

**The post-operative care described here is considered standard of care for this procedure (except for the study drug, telephone call, study diary, and questionnaires) and not related to the study.**

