#### **A.7. Study Endpoints**

The study will be concluded once each patient achieves radiographic union at 12 weeks (please refer to grading scale in the statistical consideration section) or up to six months, whichever comes first. If a patient experiences a serious adverse event, requiring them to discontinue the study medication, they will be immediately withdrawn from the study, treated appropriately, and reported.

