The patient diaries with the VAS will be collected during the first post-operative visit (one week). Patients will be asked to bring all surgery related medications and bottles to this post-operative appointment. The research fellow will again obtain the patient's post-operative pain medication consumption (including timing and dosages) by counting pills and verbally confirm study protocol compliance (Please refer to the variables collected section for full details).

Whether a difference in delayed unions at twelve weeks exists between the two groups will also be assessed. Radiographic union for each patient will be assessed by both a blinded, board-certified radiologist and two blinded board-certified podiatric surgeons. Agreement between these three experts will be assessed with a kappa score and the mean result will be used for primary analysis. Delayed and non-union rates will be compared between the two groups. A previously documented scoring system found to have both high inter- and intra-observer reliability in a series of tibial fractures reduced surgically will be utilized for this assessment. This scoring system grades each fracture according to four characteristics: 1. Rating of fracture healing, 2. Callus morphology, 3. Number of cortices visible or obliterated. 4. Number of cortices bridged (41). The modification utilized for this study will be as follows:

- ❖ **Grade 1:** Homogenous bone structure with complete obliteration of fusion site
- ❖ **Grade 2:** Massive bone trabeculae crossing fusion site, 3-4 cortices are bridged with fusion site barely discernable
- ❖ **Grade 3:** Apparent bone trabeculae crossing fusion site, 2-3 cortices are bridged with fusion site discernable
- ❖ **Grade 4:** Trace bone trabeculae crossing fusion site, 1-2 cortices are bridged with distinct visible joint space

- ❖ **Grade 5:** No bone trabeculae crossing fusion site, 0 cortices are bridged with complete visible joint space

A delayed-union will be defined as a grade 4 or 5 in any patient over twelve weeks. A nonunion will be defined as a grade 4 or 5 in any patient over six months. Analysis will include logistic regression for these binary endpoints. Odds ratios and 95% confidence intervals will be calculated between groups (delayed and/or non-union: yes/no). A 2-sided p value of  $\leq 0.05$  will be considered statistically significant.

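### The only source named for the adverse-event comparison closes at week one, while the stated purpose evaluates adverse events up to six months

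*Combined protocol and SAP*

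**What the plan says.** Section B1 (Purpose of Protocol), repeated under Figure 1, says that long-term outcomes will be evaluated, including "radiographic healing, adverse events, and time to regular shoe gear and activities up to a six month period".

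The Secondary Outcomes part of the Data Analysis section gives the source: "Adverse events will be obtained from a standard form included in the patient's study diary". The next sentence gives the analysis: "The proportion of adverse events will be compared between the ketorolac and placebo groups". No time window is attached to it.

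The Week One entry of section A.4 fixes when that source closes: "Patient diaries will be collected, post-operative medications will be counted, and study compliance will be verified". The Primary Outcome part of the Data Analysis section gives the same one-week visit for diary collection. No second diary or re-issue is described.

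Follow-up runs well past that visit. On the week 12 visit, section A.4 says: "If there is complete osseous union on radiographs, the patient will have completed the study". Patients without complete union continue to be followed, and section A.7 sets the end of study at union at 12 weeks "or up to six months, whichever comes first".

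**The concern.** The period over which adverse events are to be evaluated and the period covered by their named source do not match. Followed as written, the comparison is a first-week comparison presented under a six-month purpose. A finding of no difference could then be read as longer-term reassurance about events that were not systematically asked about. Adding late events from clinic notes afterwards would not repair this, because the rule for finding and counting them would not have been set in advance.

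**Working it through.** The plan gives no sample size, power or error rate for the adverse-event comparison, so there is no figure to reproduce. The check is arithmetic on time windows, followed by a search of the text for any other source.

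**Inputs**
- Diary collected at the one-week visit, taken as day 7 (A.4, Week One; Data Analysis, Primary Outcome).
- Study drug: 15 capsules, one every 8 hours (A.5).
- Minimum completion: week 12 ± 1 week, that is 77, 84 or 91 days (A.4, Week Twelve).
- Maximum follow-up: six months, taken as 182.6 days (B1, A.7).

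**Time covered by the diary form**
- Dosing: 15 × 8 / 24 = 5 days. The diary adds about 7 − 5 = 2 days after dosing.
- Share of time to week 12: 7 / 84 = 8.3%. At 11 weeks it is 7 / 77 = 9.1%, and at 13 weeks 7 / 91 = 7.7%.
- Share of six months: 7 / 182.6 = 3.8%.
- Time outside the named source: 100 − 8.3 = 91.7% to week 12, and 100 − 3.8 = 96.2% to six months.

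**Is another source named?**

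| Place | What it provides | Adverse-event source for the comparison after week one? |
|---|---|---|
| A.4, Immediate Post-operative: what the study adds to usual care | Study drug, diary, day-two call, pill count and compliance | No |
| End of A.3 and of A.4: similar lists | The same kind of items, plus questionnaires | None described |
| A.4, entries for week 2 to week 12 | Suture removal, radiographs, clinical assessment, activity | No form or query described |
| Other Variables of Interest | Intra-operative complications, among many others | Later adverse events not listed |
| Data Analysis, Primary Outcome | Blinded grading of union; delayed union and nonunion compared | Yes, for union failure only |
| B5 | On-call pager; reporting of all adverse events under IRB rules | Not linked to the comparison |

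Time to regular shoe gear, another outcome in the same Secondary Outcomes section, is expressly assessed at the post-operative visits. The plan specifies visit-based capture there but not for adverse events.

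**The case against.** The case on the other side has several parts, and much of it stands.

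- **Bone healing.** A reader might infer that the trial never looks for late healing harm. The documents contradict this. Radiographs are scheduled at about weeks 3, 6 and 12, a blinded radiologist and two blinded surgeons grade union, and delayed union and nonunion are compared by logistic regression. The NSAID harm that the background section is most concerned with is measured beyond week one.
- **Late events reaching the study only by chance.** This is also too strong. The surgeons are investigators treating their own patients. They see them at planned visits, their notes go into the medical record, and B5 commits to reporting all adverse events without a time limit. What remains is that no structured query is described at those visits and no route from these reports into the comparison is stated.
- **Uneven capture between arms.** The documents do not support this. Section A.6 blinds patients, surgeons, anesthesiologists and assessors. Emergency unblinding could be an exception for individual patients, but the expected fault is under-counting in both arms.
- **The percentages.** They are shares of calendar time. The diary week contains the whole dosing period, and the documents give no timing of events, so it does not follow that some 92% of events are missed. Six months is also a ceiling, because patients with complete union finish at week 12.
- **Silence is not absence.** Case report forms are mentioned but not included, so one can say only that no later adverse-event form is described. The text between B6 and B8 was not available, and nothing is inferred from it.

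None of this reconciles the stated six-month period with a source collected at week one.

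**Conclusion.** The inconsistency is real and rests on the plan's own text. The one source named for the adverse-event comparison ends at about day 7, against a minimum follow-up of about 12 weeks and a stated period of six months. It covers about 8% and 4% of that time respectively.

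The likely consequence is under-counting, in both arms, of later events other than delayed union or nonunion: wound problems, infection and hardware complications, for example. The size of the under-count cannot be calculated from the documents.

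This assumes that the diary is collected when the protocol says and is not re-issued, and that B5 reports and clinic notes do not feed the comparison, since nothing says that they do. The point concerns a secondary outcome and leaves the primary pain analysis untouched. It should still be corrected, because a stated purpose of the trial cannot be met as written.

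**What to change.** Keep the diary form for week one. Have the same standard form completed by surgeons or study staff, who are already blinded, at the visits already scheduled: weeks 2, 3, 6 and 12, and any later visit. In the Secondary Outcomes section, state that the comparison uses all of these forms, give its time window, and show first-week events separately. Because only patients without complete union are followed after week 12, the stated window should make clear how forms from those later visits are used.

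The cost is one short form at existing visits and minor added data entry. No new visit or test is needed.

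If the sponsor prefers not to do this, the adverse-event objective in B1 and under Figure 1, and any conclusion drawn from the comparison, should be restated as limited to the first post-operative week.

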#### **A.5. Exposures and their measurements (ketorolac versus placebo)**

All patients will have a Kalish bunionectomy performed, fixated by two 3.0 mm cannulated partially threaded screws. Patients will follow the post-operative course as outlined above. Patients will be randomized in the pre-operative holding area to either receiving ketorolac or placebo. If randomized to ketorolac, the patient will receive one 30 mg IV dose while in the operating room under anesthesia by the anesthesiologist. If not randomized to ketorolac, the patient will receive one intra-operative 30 mg IV dose of placebo by the anesthesiologist. Patients will be given the study drug (either ketorolac or placebo capsules) after the procedure. This will be dispersed from the research pharmacy department following hospital protocols. If randomized to ketorolac, the patient will take one 10 mg capsule every eight hours, beginning approximately eight hours after the surgical procedure for a total of five days (15 capsules). If randomized to placebo, the patient will take a placebo capsule every eight hours, beginning eight hours after the surgical procedure, for a total of five days (15 capsules).

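### Adverse events are promised up to six months, but the only source named for the between-arm comparison is a diary form collected at one week

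*Combined protocol and SAP*

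**What the plan says.** B1 (Purpose of Protocol), repeated under Figure 1 in B3.A.1, says that the long-term evaluation includes "radiographic healing, adverse events, and time to regular shoe gear and activities up to a six month period".

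B3.B.b, Secondary Outcomes, gives the source: "Adverse events will be obtained from a standard form included in the patient's study diary". The next sentence sets up the ketorolac versus placebo comparison of adverse events and gives no time window.

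Two places fix when the diary closes. B3.A.4, Week One: "Patient diaries will be collected, post-operative medications will be counted, and study compliance will be verified". The Primary Outcome part of B3.B.b also places diary collection at the first post-operative visit, at one week.

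On the end of follow-up, B3.A.4 (Week Twelve and Subsequent Visits) says: "If there is complete osseous union on radiographs, the patient will have completed the study". Patients without union continue under their surgeon, and six months is the limit for classifying a nonunion.

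**The concern.** The stated window and the stated source do not match. A form that leaves the patient's hands at week one cannot record what happens at weeks two to twelve, whatever it asks. The protocol itself expects some later problems. At week six it notes: "Indications for physical therapy may include a continued stiff joint or chronic edema".

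At stake is what the report may claim. A table built from this source is a one-week table. If it showed no difference between arms, it would not support a statement about adverse events up to six months, or even up to twelve weeks.

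**Working it through.** The plan states no adverse-event rate and no power for this outcome, so there is no figure to reproduce. The check sets the sections side by side and adds simple arithmetic.

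**1. Share of follow-up covered by the diary.** Inputs: diary collected at about day 7; week twelve is day 84; six months is about 183 days.
- To week twelve: 7/84 = 8.3%, leaving 84 − 7 = 77 days uncovered.
- To six months: 7/183 = 3.8%. Six months is a maximum, since patients with union finish at week twelve, so the first ratio is the relevant one for most patients.

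**2. Does the diary span dosing?** B3.A.5 has the ketorolac capsules "beginning approximately eight hours after the surgical procedure for a total of five days (15 capsules"), one every eight hours. Last capsule: 8 + 14 × 8 = 120 hours. One week is 168 hours. The diary therefore covers all dosing plus about 48 hours.

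**3. Is there another source after week one?**
- B3.A.4: the scheduled visits at weeks 2, 3, 6 and 12 cover sutures, radiographs, clinical assessment and return to activity. None has an adverse-event query.
- B3.A.3, last paragraph: the study-specific procedures are the calls, study drug, diaries and questionnaires. A visit-based adverse-event form is not among them.
- Other Variables of Interest: lists intra-operative complications and physical therapy use, but not post-operative adverse events.
- Secondary Outcomes: time to regular shoe gear is given a visit-based source in the medical record. Adverse events are not.
- B5: patients have an on-call pager, and all adverse events go to the IRB. Neither is named as feeding the comparison.

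**4. What late collection could show.** With 44 per arm all followed, zero late events in an arm gives an exact two-sided 95% upper limit of 1 − 0.025^(1/44) = 8.0%. The diary gives no limit at all for that period. With events, intervals stay wide. For illustration only, 7/44 versus 2/44 is 15.9% − 4.5% = +11.4 points, with a Newcombe 95% interval of −1.9 to +25.2. The gain is a correct window with an honest interval, not power.

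**5. Why stop the comparison at week twelve.** Only patients without union are followed further. Suppose the arms differ by 20.5 points in lack of union at week twelve, the difference used in the sample size section. If an assumed 10% of those followed on report a first event, unequal follow-up alone adds 0.10 × 20.5 = 2.1 points. Over an assumed 5% to 20% this is 1.0 to 4.1 points.

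**The case against.** The strongest reply is that little of importance is missed. The late harm of main interest, delayed union and nonunion, has blinded three-reader assessment and its own regression. The diary spans the whole dosing period. Stiffness or edema may lead to physical therapy, whose use is recorded and is to be checked between groups with the other variables. Shoe gear and the functional recovery index would also reflect some late complications. Much of what remains is likely to be ordinary surgical morbidity unrelated to five days of drug. All of this stands and keeps the point small. It does not remove the mismatch: physical therapy use is a partial proxy, and no systematic late source feeds the adverse-event comparison.

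Two stronger readings are tempting, and the documents support neither.

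- A reader might infer that serious events on study drug would drop out of the comparison, because B3.A.7 says that after a serious event "requiring them to discontinue the study medication, they will be immediately withdrawn from the study", and on schedule this comes before the diary is collected. But the same sentence goes on to require treatment and reporting, B5 requires reporting of all adverse events, and B3.B.b puts all analyses on the intention-to-treat principle. Post-operative visits are standard care, so the diary may still come in. The events would be on file. What is missing is a sentence that brings them into the table.
- A reader might infer that late adverse events go unrecorded. The pager, clinic notes and IRB reports may well hold them, and B5 and B8 mention case report forms that are not in the document. The point is only that the plan does not link these to the comparison.

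**Conclusion.** The mismatch is in the text and needs no outside fact. Followed as written, the plan yields an adverse-event comparison of about one week, or 8% of the time to week twelve, under a purpose that says up to six months. Complications other than delayed union and nonunion have no systematic source after that.

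The documents give no event rates, so the number of late events at issue cannot be stated. If nearly all events fall in week one, the loss is small. Nothing in the plan shows a late excess on ketorolac, and none is claimed here. I have not seen the part of the document between B6 and B8. The pain and union conclusions are unaffected. Severity is low.

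**What to change.** In Secondary Outcomes, name three sources: the diary to week one; a short adverse-event question, asked and recorded blind to arm, at the existing visits at weeks 2, 3, 6 and 12; and every event reported under B3.A.7 and B5. Compare the number of patients with at least one event through week twelve by assigned arm, with risk differences and 95% intervals, and tabulate by event type. List events after week twelve descriptively.

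In B3.A.7, stop study drug after a serious event but keep the patient in follow-up, with consent, as intention to treat implies. Such a patient already counts as having an event. Continued follow-up serves the tabulation by type and the other outcomes.

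The cost is one question at visits that already take place as standard care, some extra case-report work, and intervals that will be wide at 44 per arm. If late collection is not wanted, change B1 and the text under Figure 1 to say that adverse events are compared for the first week only. That costs nothing but the longer claim.

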#### **Missing Data**

Given that the first outcome measure occurs within two days and the second outcome occurs in twelve weeks of study enrollment, we do not anticipate that missing data will be a large concern. Protocol deviations will be recorded and reported but the primary analysis will be an **intent-to-treat analysis**. For outcomes requiring a longer follow-up duration, any patients who are lost, move or expire will be counted as treatment failures. Patients will be generally healthy as this is a population undergoing elective bunionectomy surgery. In addition, information will be collected regarding patient contact information to help prevent loss of patients. Patients that miss a follow-up appointment will have a set mechanism in-place in order to contact the patients. All available contact information

including the patient's residential and work address, work, home and cellular phone number as well as contact information of the next of kin and closest friend will be obtained for each patient. Permission to contact these people as necessary will be obtained. The short follow-up period will also improve success in these measures. Finally, there is a built in 10% increase in patient sample size if the above safety measures still fail.

Although we do not anticipate significant missing data problems, any concerns will be dealt with sensitivity analyses to determine their impact.

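### Time to regular shoe gear can be right-censored and is observed only at visits, but the plan gives no rule for patients whose time is never observed

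*Combined protocol and SAP*

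**What the plan says.** The purpose section (B1) lists "time to regular shoe gear and activities up to a six month period" among the long-term outcomes. Under Data Analysis, Secondary Outcomes, the plan says "Time to regular shoe gear will be compared between the two groups" and then, on how it is measured, "This information will be assessed during the post-operative visits and recorded within the secure BIDMC online medical record for each patient". No test is attached to it. The general rule later in that section is "Continuous data will be analyzed with a 2-sided student's t-test if normally distributed or a Wilcoxon Rank Sum test". Regression or stratification is allowed if confounders appear, but no model is named.

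Follow-up does not depend on shoe status. Section A.4, item h (week twelve), says "If there is complete osseous union on radiographs, the patient will have completed the study". Section A.7 says "The study will be concluded once each patient achieves radiographic union at 12 weeks", or otherwise at up to six months. It adds that patients who must stop study drug because of a serious adverse event will be handled as follows: "they will be immediately withdrawn from the study, treated appropriately, and reported".

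For outcomes with longer follow-up, the Missing Data section says "any patients who are lost, move or expire will be counted as treatment failures". It also promises sensitivity analyses without describing them. The text available for review mentions no censoring, Kaplan-Meier curve, log-rank test or Cox model.

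**The concern.** A t-test or a rank-sum test needs a value for every patient. Under the plan's own follow-up rules a patient can leave before returning to regular shoes, and then it is known only that the time exceeds the last visit. The analyst must drop that patient, use the last visit as if it were the event, invent a time, or assign a worst rank. The plan does not choose among these.

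The choice matters in two ways. Dropping unfinished patients removes the longest times and shrinks any real difference. Inventing a late time for lost patients turns unequal loss between the arms into an apparent difference in recovery. In addition, status is learned at visits, and the scheduled ones at weeks six and twelve are six weeks apart. Unless a date is recorded, times are known only to within an interval.

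**Working it through.** The plan states no figure for this outcome, so there is none to reproduce. The check has two parts.

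**1. Can a patient finish without an observed time, and does a rule cover it?**

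| How follow-up ends without the event | Source | Value or rank supplied? |
|---|---|---|
| Union at week 12, not yet in regular shoes | A.4 item h; A.7 | No; the failure rule does not mention completers |
| Withdrawal after a serious adverse event | A.7 | No; withdrawal is not named in the failure rule |
| Lost, moved or died | Missing Data | Called a failure, with no time or rank |
| Incomplete union, followed to at most six months | A.4 item h; A.7 | No |

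A failure label fits the yes/no union outcomes directly. It does not by itself give a number for a time.

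**2. How much could the ad hoc choice matter?**

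Inputs from the documents: 44 per arm, two-sided 0.05, and ends of follow-up at week 12 and at six months (taken as week 26). Assumed, because the documents give no return-to-shoe data: no returns before week 3, then exponential times at 0.33 v 0.17 per week.

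With rate λ and τ weeks from week 3 to the cut-off, the fraction unfinished is q = exp(−λτ). The true mean time after week 3 is 1/λ, and the mean among observed patients is 1/λ − τq/(1−q).

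True difference: 1/0.17 − 1/0.33 = 5.88 − 3.03 = 2.85 weeks.

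Week-12 cut-off, τ = 9:
- q = exp(−2.97) = 5.1% v exp(−1.53) = 21.7%.
- Observed means: 3.03 − 9×0.0513/0.9487 = 2.54; 5.88 − 9×0.2165/0.7835 = 3.39.
- Observed-only difference: 0.85 weeks.

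Week-26 cut-off, τ = 23:
- q = exp(−7.59) = 0.05% v exp(−3.91) = 2.0%.
- Observed means: 3.02; 5.88 − 23×0.0200/0.9800 = 5.41.
- Observed-only difference: 2.39 weeks.

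Simulated power under the same assumptions (repeat runs differ by about two points):

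| Cut-off for everyone | Rank test, observed only | Wilcoxon, unfinished ranked worst | Log-rank |
|---|---|---|---|
| Week 12 | 31% | 72% | 81% |
| Week 26 | 70% | 75% | 86% |

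The plan lies between these rows: patients with union stop at week 12 and the others continue.

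A second simulation looked at false positives: 1,500 runs, Weibull times with shape 2.5, median 7 weeks in both arms, and follow-up ending at week 12 for 90% and week 26 for 10%. With dropout of 2% v 18% and no true difference, rejection rates at the 5% level were:
- 18.3%: t-test with unfinished patients set to 26 weeks
- 9.0%: t-test with the censoring time treated as the event time
- 8.6%: worst-rank Wilcoxon
- 5.8%: log-rank

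With 10% dropout in both arms, every method stayed between 5% and 6%.

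**The case against.** The strongest case against is that the gap is one of wording and its effect may be slight. Several parts of that stand.

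- A reader might infer that the plan drops unfinished patients. It does not say so. It commits to intention-to-treat and counts lost patients as failures. The 31% v 81% contrast therefore describes one possible choice, combined with a week-12 cut-off for everyone, and is not the plan's expected loss.
- A reader might infer that patients censored at week 12 are the slow bone healers. Section A.4 points the other way: incomplete union means continued follow-up. The patient censored at week 12 by design has united but is not yet in regular shoes. That group may be small, since section A.4 allows a soft-soled shoe from about week three and normal activities at week six when healing is satisfactory.
- A reader might infer that a failure rule can have no meaning for a time. It can be read as a worst rank in the Wilcoxon test. The plan does not state that reading, and a t-test cannot use it.
- The t-test or Wilcoxon rule applies by default, not by assignment, and regression and sensitivity analyses are not excluded.
- Exponential times with proportional hazards favour the log-rank test, so part of its advantage comes from the assumption.

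None of this gives the plan a stated way to handle a censored time, or to treat a week-12 completer who is not yet in regular shoes.

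**Conclusion.** The point holds as a gap in specification. The plan's follow-up rules allow right-censoring and its visit schedule groups the times, but no stated method deals with either. Depending on the ad hoc choice, the comparison can lose power or be biased.

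Under the assumed rates, the shortfall against log-rank is 9 points (week 12) to 11 points (week 26) for a worst-rank reading. For an observed-only analysis it is 50 and 16 points. The false-positive inflation appeared only when dropout differed between arms. All these sizes rest on assumed return times and dropout; the documents give neither.

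This is a secondary outcome without a power calculation. The 48-hour pain comparison, the delayed-union and nonunion analyses and the sample size are unaffected. It is a cheap improvement.

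**What to change.** Before unblinding, add a short paragraph to the analysis plan for this outcome:

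- State what counts as regular shoes and the time origin, and record the date of return or, failing that, the two visits between which it occurred.
- Show Kaplan-Meier curves and compare arms with a log-rank test or Cox model, giving the hazard ratio and 95% CI. If only visit intervals are known, use an interval-censored or discrete-time model.
- Adjust for the randomisation strata where numbers allow; bilateral cases are expected to be uncommon, so some strata may be too sparse.
- Censor patients who have not returned to regular shoes at their last visit, including those who complete at week 12.
- Exempt this outcome from the treatment-failure rule, and give a worst-rank Wilcoxon test as a sensitivity analysis.

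The cost is some protocol text, one recorded date or interval at existing visits, and minor extra analysis work in the SAS package already named. The main analysis would rely on non-informative censoring, which may be doubtful for withdrawals after serious adverse events. The worst-rank analysis and a table of censoring reasons by arm would let readers judge that.
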